## **Abstract**

### **Background**

Atrial fibrillation (AF) is the most common sustained arrhythmia and the number of patients with AF is expected to increase substantially in the coming decades. One third of patients with AF report no AF-associated symptoms, but up to one-fourth report severe symptoms. It is unclear why patients' experience of AF-related symptoms varies so much. We have previously shown that patients with symptomatic AF exhibit lower pain tolerance than patients with asymptomatic AF, as well as impaired pain inhibitory control and facilitated summation of pain, indicating that pain sensitisation may be of importance in symptomatic AF. In patients with chronic pain conditions, several biomarkers and epigenetic markers associated with generation and /or maintenance of chronic pain have been identified. Previous research of biomarkers and epigenetic markers associated with pain is sparse in patients with AF.

### **Objective and methods**

To study levels of biomarkers and epigenetic markers in blood in patients with symptomatic paroxysmal AF (n=100), in relation to severity of AF symptoms, and compared to age- and sex-matched controls without AF (n=100). Blood will be obtained before and after AF ablation and levels of biomarkers, epigenetic markers and cardiac and inflammatory markers, analysed. Patients will complete an AF-specific symptom and a generic health-related quality of life questionnaire.

### **Clinical relevance**

In the future, biomarkers and epigenetic markers associated with pain may be used as a tool for evaluation of patients with AF and have an impact on individualized management.

Another possibility is a rationale for future studies of novel analgesics that neutralize biomarkers or antagonizes its receptors.

### **Trial Registration**

The study protocol will be registered at ClinicalTrials.gov after approval by the Swedish Ethical Review Authority.

### **Keywords**

Atrial fibrillation, Symptoms, Quality of life, Pain

## **Abbreviations**

|       |                                     |
|-------|-------------------------------------|
| AF    | Atrial fibrillation                 |
| AF6   | Atrial fibrillation 6 questionnaire |
| DNA   | Deoxyribonucleic acid               |
| ECG   | Electrocardiogram                   |
| NGF   | Nerve growth factor                 |
| RNA   | Ribonucleic acid                    |
| SF-36 | Short form 36 health survey         |

## **Introduction**

### **Atrial fibrillation**

Atrial fibrillation (AF) is the most common sustained arrhythmia affecting approximately 3% of adults aged 20 years or older in Western countries, and is expected to increase further in the coming decades(1). The presence of AF is independently associated with an increased risk of all-cause mortality and morbidity, largely due to stroke and heart failure, dementia, symptoms, and impaired quality of life(2-7). The management of AF aims to prevent AF-related complications using oral anticoagulation therapy in patients with a high risk of stroke and to reduce symptoms and improve health-related quality of life using a rate (slowing of the ventricular rate) or rhythm control (restoration and maintenance of normal sinus rhythm) strategy(8).

About one third of patients with AF have no AF-associated symptoms, but up to one-fourth of patients report severe symptoms such as palpitations, dyspnea, chest discomfort or pain, dizziness and syncope(9-11). In addition, one third of patients with symptomatic AF suffer from psychological distress(11, 12). It is well recognized, but unclear why patients' perception of AF varies so much. Several studies have evaluated the relationship between patient characteristics and the presence of AF symptoms and have found that symptomatic AF is more frequent in women than in men, and in younger age(13, 14). Inconsistent results have been reported for associations between symptomatic AF and comorbidities(15). Furthermore, symptoms are more common in patients with paroxysmal and persistent AF than in patients with permanent AF(16). However, asymptomatic AF episodes are common even in highly symptomatic patients and AF interventions such as AF ablation increase asymptomatic episodes(17). In conclusion, little is known of the pathophysiological

mechanisms underlying AF symptomatology but both somatic and psychological factors are likely involved.

### **Pain mechanisms**

Patients with chronic pain conditions such as osteoarthritis, chronic pancreatitis and irritable bowel syndrome, show a high degree of central sensitisation, i.e. facilitated pain responses to repeated painful stimulation and impaired conditioned pain modulation (CPM) compared with controls(18-21). Furthermore, these patients often show a discrepancy between pain intensity and objective measures of disease severity and healthcare personnel often underestimate patients' pain intensity(22, 23). It is also well-known that stress influences pain sensitivity and has been correlated to hyperalgesia in patients with ischemic heart disease(24, 25). The importance of pain sensitisation in visceral ailments such as AF is emerging, and the authors have previously shown that patients with symptomatic permanent AF exhibit both impaired pain inhibitory control as well as facilitated summation of pain, and therefore, pain sensitisation(26).

### **Biomarkers**

Biomarkers associated with chronic pain, such as nerve growth factor (NGF), are proteins fundamental during embryonal development for the growth, differentiation, and survival of sensory and sympathetic afferent neurons. During adulthood, they have been found to play a key role in the modulation of nociception through short- (direct sensitisation of peripheral nociceptors) and long-term (changes of gene expression in the dorsal root ganglion) effects. These modifications lead to a wider input from peripheral nociceptors resulting in increased signaling to the central nervous system(27), (28). AF ablation has been shown to increase the plasma level of NGF in humans in the days following the procedure(29), and chronic high

levels of NGF and noradrenaline increased the incidence of inducible AF and its duration in animal studies(30). The use of monoclonal NGF antibodies has been administered to patients with osteoarthritis, providing a significantly greater pain relief compared to NSAIDs and opioids(31).

### **Epigenetic markers**

Epigenetic mechanisms such as DNA methylation, covalent histone modifications, and non-coding RNAs, have been observed to play an important role as mediators of long-term changes in central and peripheral nervous systems in chronic pain. Epigenetic markers can be measured in blood or tissue(36-37). To our knowledge, pain-related epigenetic markers have not been analysed in patients with AF.

### **Purpose**

To study levels of biomarkers and epigenetic markers associated with pain as well as cardiac and inflammatory biomarkers in patients with symptomatic paroxysmal AF, in relation to severity of AF symptoms, and compared to age- and sex-matched controls without AF.

### **Hypothesis**

We hypothesize that

1. Biomarkers and epigenetic markers increase with AF severity
2. Patients with symptomatic AF display increased levels of biomarkers compared with controls, thereby further proving the involvement of central sensitisation mechanisms in patients with symptomatic AF

## **Clinical relevance**

In the future, biomarkers and epigenetic markers associated with pain could be used as tools for evaluation of patients with AF, and have an impact on individualized patient management. Treatment may include medication that neutralizes the biomarker or antagonizes its receptors.

## **Material and methods**

### **Study design**

Single-center cohort study, Örebro University Hospital.

### **Subject inclusion criteria**

Consecutive study participants will be recruited from the waiting list of all patients planned for AF ablation (pulmonary vein isolation) in Örebro University Hospital. Only patients with symptomatic AF are planned for AF ablation.

Further inclusion criteria:

- Male or female subject  $\geq$  20 years and  $\leq$  75 years
- Paroxysmal AF (AF that terminates spontaneously or with intervention within 7 days (8))
- Written informed consent

### **Subject exclusion criteria**

- Persistent AF (AF that is continuously sustained beyond 7 days, including episodes terminated by cardioversion after  $\geq$  7 days(8))

- Previous pulmonary vein isolation
- Cognitive or psychiatric condition
- Diabetes mellitus
- Ischemic heart disease
- Heart failure
- Asthma
- Pregnancy
- Previous/current drug or alcohol abuse
- Previous neurological or concomitant musculoskeletal disorders
- Continuous analgesic medication

### **Patient consent and inclusion**

All potential patients will receive written information about the study and at the standard physician visit the day before the AF ablation, be asked to participate in the study. After obtaining written informed consent, patients will be asked to complete the Atrial fibrillation 6 questionnaire (AF6) and the Short form 36 health survey (SF-36) questionnaires before a 12-lead ECG is obtained. Comorbidities, medications and duration of AF will be documented and a routine clinical examination will be performed, and the modified European Heart Rhythm Association symptoms scale assessed.

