### **Control group**

Sex and age-matched controls will be recruited by advertisement. The same blood samples will be obtained from controls as on patients with AF but only once, and controls will be asked to complete the SF-36 questionnaire and a questionnaire about previous and current diseases and current medication.

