### ***Statistical analysis***

Data will be presented as mean and standard deviation. Independent t-test will be used to compare biomarkers and epigenetic markers in AF patients and control subjects. Pearson correlations will be used for linear estimates and Spearman's correlations for non-linear parameters. Multiple linear regression analysis will be performed to show associations between explanatory variables (age, sex, symptoms) and biomarkers and epigenetic markers associated with pain. Analyses will be performed using IBM SPSS Statistics 22 (Armonk, NY, USA) or STATA release 14 (College Station, TX, USA).

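### Diseases that are not exclusion criteria are recorded in patients and controls but enter no stated analysis, so a comorbidity imbalance could create or mask an AF-versus-control difference

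*Combined protocol and SAP*

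**What the plan says.** Disease history is collected on both sides. Under Patient consent and inclusion, the plan for AF patients reads "Comorbidities, medications and duration of AF will be documented and a routine clinical examination will be performed". Under Control group, "controls will be asked to complete the SF-36 questionnaire and a questionnaire about previous and current diseases and current medication".

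The groups come from different sources. Patients are taken consecutively from the hospital's ablation waiting list (Subject inclusion criteria). For controls, "Sex and age-matched controls will be recruited by advertisement". No other matching factor is named.

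Under Statistical analysis, the group comparison is this: "Independent t-test will be used to compare biomarkers and epigenetic markers in AF patients and control subjects". The multiple regression is to show "associations between explanatory variables (age, sex, symptoms) and biomarkers and epigenetic markers associated with pain". The only other association method is bivariate: "Pearson correlations will be used for linear estimates and Spearman's correlations for non-linear parameters". The Secondary endpoint section adds AF duration and health-related quality of life, but not comorbidity.

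The exclusion criteria remove diabetes, ischemic heart disease, heart failure, asthma, psychiatric, neurological and musculoskeletal conditions, and continuous analgesic use. They do not list hypertension or thyroid, kidney or non-musculoskeletal inflammatory disease.

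**The concern.** This is a non-randomised comparison. Matching on age and sex does not equalise other disease between people awaiting a hospital procedure and people who answer an advertisement. If a non-excluded condition is more common in one group and shifts a marker, the t-test counts that shift as part of the group difference. The cardiac and inflammatory markers named under Purpose are not specific to AF.

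The interpretation is at stake. Hypothesis 2 would take higher biomarker levels in patients as further evidence that central sensitisation is involved in symptomatic AF. An unadjusted difference cannot separate that reading from a difference in comorbidity. The bias can run either way: it can generate a difference where there is none, or cancel a real one.

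The plan intends to hold the data needed to examine this, and does not say they will be used.

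**Working it through.** **Is comorbidity used anywhere?** Setting the sections side by side:

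| Step in the plan | Variables named | Comorbidity? |
|---|---|---|
| Matching (Control group) | age, sex | no |
| t-test (Statistical analysis) | group | no |
| Correlations (Statistical analysis) | not named; bivariate | no adjustment possible |
| Multiple regression (Statistical analysis) | age, sex, symptoms | no |
| Secondary endpoint | age, sex, AF duration, quality of life | no |

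No matching, adjustment, stratification or sensitivity analysis on comorbidity is described.

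**How large could the effect be?** The documents state no alpha, power, effect size, SD, disease prevalence or disease effect, so there is no figure of the plan's own to reproduce.

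*Input from the Abstract:* 100 patients and 100 controls.
*Assumptions:* two-sided alpha 0.05, no true AF effect, a disease prevalence difference Δp and a disease effect e on the marker in SD units.

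Bias of the unadjusted difference = Δp × e. Standard error = √(2/100) = 0.1414 SD. Noncentrality λ = bias / 0.1414. The rejection rate comes from the noncentral t with 198 df (critical value 1.972).

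| Δp (assumed) | e (assumed) | Bias | λ | False-positive rate |
|---|---|---|---|---|
| 0 | – | 0 | 0 | 5.0% |
| 0.20 | 0.3 SD | 0.06 SD | 0.424 | 7.1% |
| 0.25 | 0.4 SD | 0.10 SD | 0.707 | 10.8% |
| 0.30 | 0.5 SD | 0.15 SD | 1.061 | 18.4% |

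*Cross-check.* A normal approximation that allows for the extra variance from the disease mixture gives 7.0% for 50% v 30% with 0.3 SD, 10.6% for 50% v 30% with 0.5 SD (bias 0.10 SD), and 17.9% for 50% v 20% with 0.5 SD. A 4,000-run simulation of the last case rejected in 18.5% of runs with the t-test and in 4.7% with a model containing group and the disease.

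*Sensitivity to the assumptions.* A weak case (40% v 30%, 0.3 SD) gives 0.03 SD and 5.5%. An extreme one (60% v 20%, 0.8 SD) gives 0.32 SD and 56.8%.

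**Masking.** Take a true difference of 0.40 SD, roughly what 100 per group detects with 80% power. Without bias, λ = 0.40/0.1414 = 2.828 and power is 80.4%. Bias in the opposite direction leaves these apparent differences:
- 0.06 SD of bias: 0.34 SD, power 66.7%
- 0.10 SD: 0.30 SD, power 56.0%
- 0.15 SD: 0.25 SD, power 42.1%

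**Symptom severity (n=100).** If comorbidity correlates with both AF6 and a marker at 0.2, 0.3 or 0.4, the induced correlation is the product: 0.04, 0.09 or 0.16. By Fisher's z (SE = 1/√97) the false-positive rate is 6.8%, 14.4% or 35.6%. These correlations are also assumed.

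**The case against.** **Restriction already does part of the work.** This stands. The exclusion list removes several major conditions, and no section says that hypertension or any other remaining disease shifts a pain marker or differs between the groups. The Control group section does not say whether the exclusions apply to controls. If they do not, more imbalance is possible, but the point does not depend on that.

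**The inputs are assumed and the bias may be small.** This also stands. Biases of 0.06 to 0.15 SD are below the roughly 0.40 SD detectable at 80% power, and the low case moves the error rate only from 5% to 7%. A reader might infer from the table that the t-test will produce false AF effects. The documents do not support that: they fix neither the size nor the direction of the bias.

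**An unadjusted comparison answers the objective as worded.** The second primary objective asks only for differences in level. That is fair, but hypothesis 2 attaches a mechanism to the difference, and the t-test cannot carry that step.

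**Symptom severity.** A reader might infer that comorbidity confounds the symptom analysis just as strongly. The text is thinner here. The regression is not assigned to an objective or limited to patients. The Introduction says only "Inconsistent results have been reported for associations between symptomatic AF and comorbidities", in a discussion of whether symptoms are present, whereas every study patient is symptomatic and the objective concerns severity. That supports a sensitivity analysis and no more.

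**Adjustment is imperfect.** Patients are assessed at a physician visit and controls report for themselves, so a shared checklist will not fully equalise ascertainment. Medications are recorded in both groups and equally unused, so adjusting for disease does not isolate AF from its treatment.

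**Conclusion.** The gap is in the text: diseases outside the exclusion list are recorded in both groups, and no stated analysis uses them. This goes beyond missing detail, because the plan names a specific unadjusted test for a non-randomised comparison between differently recruited groups.

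The consequence is a possible bias of unknown size and direction in the AF-versus-control comparison. Under the three assumed combinations of prevalence difference and disease effect, the false-positive rate per marker would be about 7%, 11% or 18% instead of 5%. Bias of the same size in the opposite direction would reduce power. These figures rest wholly on assumed inputs, alpha included. The symptom-severity analysis is a secondary part of the point. The change should be made, since it is cheap and uses information the study already intends to collect.

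**What to change.** 1. In Patient consent and inclusion and in Control group, record diseases with the same checklist, and report them by group.
2. In Statistical analysis, keep the t-test and add a pre-specified linear model for each marker with group, age, sex and a short named list of non-excluded conditions, with hypertension as a minimum. Name the conditions before any marker data are seen. Use named conditions, not an unweighted disease count, which would treat unlike diseases as equal and could differ by group through ascertainment alone.
3. As a secondary sensitivity analysis, add the same conditions to the age, sex and symptoms regression, fitted in patients.
4. Report adjusted and unadjusted estimates together with confidence intervals, and state that a difference will not be attributed to AF on the t-test alone.

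The cost is one common checklist, a few degrees of freedom (200 participants for the group model, 100 for the symptom model) and slightly wider intervals. No extra visits, blood or participants are needed. Some residual bias remains because disease is physician-assessed in patients and self-reported in controls; the report should say so.

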### ***Blood samples***

Blood samples for biomarkers and epigenetic markers associated with pain, cardiac biomarkers, and inflammatory markers, will be obtained when standard blood samples are taken the day before the ablation, and the day after ablation. In total 30 ml of blood per time will be obtained. In controls, the same blood samples will be obtained once only. Blood

samples will be stored in a biobank for possible later analysis. Blood samples may be analysed in another laboratory in Sweden or in the EU/ESS.

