### ***AF severity assessment***

The patient-reported AF6 questionnaire includes six items (breathing difficulties at rest and upon exertion, limitations in day-to-day life, feeling of discomfort, tiredness and worry/anxiety due to AF) and a score of 0 (no symptoms) to 10 (severe symptoms) is reported for each item, and all scores are added into a single sum score. Sum scores range from 0 to 60, with higher values reflecting more severe AF-related symptoms. The AF6 includes a recall period of the last 7 days(32, 33).

The physician-assessed modified European Heart Rhythm Association symptoms scale is used for symptom severity assessment in patients with AF, relating specifically to the time when patients feel symptoms of AF. Patients in class I are considered to have no symptoms, in class IIa mild, class IIb moderate, class III severe and in class IV disabling symptoms of AF(8, 34).

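### Objective 2 cannot separate AF from being on the eve of an ablation, objective 1 may be biased by differences in anxiety between patients, and no dedicated stress measure or adjustment is planned

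*Combined protocol and SAP*

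**What the plan says.** - **Patients, timing.** Under Patient consent and inclusion, patients will "at the standard physician visit the day before the AF ablation, be asked to participate in the study". After consent, "patients will be asked to complete the Atrial fibrillation 6 questionnaire (AF6) and the Short form 36 health survey (SF-36) questionnaires". Under Blood samples, their blood samples "will be obtained when standard blood samples are taken the day before the ablation, and the day after ablation". The Follow-up section schedules no later visit, so no patient sample is taken away from the procedure.
- **Controls.** Under Control group: "Sex and age-matched controls will be recruited by advertisement". They give blood once and complete SF-36 and a questionnaire on diseases and medication. No procedure is described for them.
- **Stress.** Under Pain mechanisms: "It is also well-known that stress influences pain sensitivity and has been correlated to hyperalgesia in patients with ischemic heart disease".
- **Severity measures.** AF6 has six items, each 0 to 10, summed to 0-60 with a 7-day recall. The last four items are "limitations in day-to-day life, feeling of discomfort, tiredness and worry/anxiety due to AF". The physician-assessed modified EHRA class is also recorded and refers to the time when AF symptoms are felt.
- **Analysis.** Statistical analysis plans an independent t-test for patients against controls, correlations, and a regression on age, sex and symptoms. No stress or anxiety covariate is listed. SF-36 enters only through the secondary objective on health-related quality of life.

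**The concern.** In objective 2, every patient is within a day of an invasive procedure when sampled, and no control is described as awaiting one. A marker that responds to the stress of the setting would differ between the groups even if AF had no effect on it. The second hypothesis would read a higher level in patients as evidence of central sensitisation, and that reading is unsafe while an influence the protocol itself names differs by group and goes unrecorded.

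Objective 1 is exposed less directly. The AF6 recall always covers the week before ablation, and one of its items is worry/anxiety. A patient more anxious about the coming procedure may score higher on that item and, if the marker responds to stress, may also have a different marker level. That would produce an association that is not with AF symptoms as such.

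**Working it through.** The plan states no alpha, power, effect size or SD, so there is no figure of its own to reproduce. The overlap is read directly from the text. The numbers below only illustrate what it could do.

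**Step 1: is there any overlap between the groups in procedural setting?**

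| | Patients | Controls |
|---|---|---|
| Source | Waiting list for ablation | Advertisement |
| Blood samples | Day before and day after ablation | Once, no procedure described |
| Sample away from a procedure | None | The only sample |
| Dedicated stress measure at the draw | None | None |

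There is none. Whichever patient sample enters the t-test, AF status and closeness to ablation are the same variable. Matching on age and sex does not change this, and a larger sample would not remove it.

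**Step 2: objective 2, illustration.** Inputs from Objective and methods: patients "in patients with symptomatic paroxysmal AF (n=100), in relation to severity of AF symptoms", "compared to age- and sex-matched controls without AF (n=100"). Assumed: one marker, two-sided 5%, no true AF effect, and a setting effect that shifts patients by d SD. The t-test has 100 + 100 − 2 = 198 df, and its noncentrality is d / √(2/100) = d × √50.

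| Assumed d | Noncentrality | P(significant) |
|---|---|---|
| 0 | 0 | 5.0% |
| 0.1 | 0.71 | 10.8% |
| 0.2 | 1.41 | 29.1% |
| 0.3 | 2.12 | 56.0% |

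A normal approximation gives 10.9%, 29.3% and 56.4%. The design would have about 80% power at d = 0.40, so a setting effect of that size would look the same as a real AF effect.

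**Step 3: objective 1, illustration.** Suppose anxiety correlates a with AF6 and b with the marker, and nothing else links the two. The induced correlation is r = a × b. With n = 100, Fisher's z has standard error 1/√97, so the test statistic is centred at atanh(r) × √97.

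| Assumed a, b | Induced r | P(significant) |
|---|---|---|
| No shared anxiety effect | 0 | 5.0% |
| 0.2, 0.2 | 0.04 | 6.8% |
| 0.3, 0.3 | 0.09 | 14.4% |
| 0.4, 0.4 | 0.16 | 35.6% |

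The worry/anxiety item contributes at most 10 of 60 points, or 16.7% of the range.

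**Step 4: how much can a rating remove?** If a measure correlates q with true stress and is otherwise unrelated to AF6 and the marker, the partial correlation is (ab − aq·bq) / √[(1 − a²q²)(1 − b²q²)]. With a = b = 0.4:

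- q = 0.5: (0.16 − 0.04) / 0.96 = 0.125.
- q = 0.7: (0.16 − 0.0784) / 0.9216 = 0.089.

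An imperfect rating reduces the bias but does not abolish it.

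**The case against.** Five points can be made for the plan.

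1. **Objective 1 is not confounded by design.** A reader might infer that pre-procedural stress distorts both primary objectives alike. The documents do not support that. All patients face the same procedure, and an exposure shared equally induces no correlation among them. Bias needs differences between patients that move both AF6 and a marker. The AF6 item is also worded as anxiety due to AF, the modified EHRA class gives a second severity measure tied to symptomatic periods, and excluding psychiatric conditions may narrow the differences. This stands. It does not clear objective 1, because the Introduction reports psychological distress in one third of symptomatic patients.

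2. **Stress is not wholly unmeasured.** A reader might infer that nothing collected bears on it. Both groups complete SF-36, which yields a mental component summary, and patients answer the AF6 worry item. This stands as far as it goes. But SF-36 recalls four weeks, the worry item exists only in patients and is part of the severity score, and neither is planned as an adjustment.

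3. **The link to the markers is inferred.** The protocol ties stress to pain sensitivity, not to marker levels, and describes epigenetic mechanisms as mediating long-term changes. A reader might conclude that the bias must favour the hypotheses. That would follow only for a marker that rises with stress. This stands.

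4. **The error rates are ordinary power at assumed shifts.** Any confounder of that size would give them. This stands, and they are offered only as illustration.

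5. **Anxiety is partly AF symptomatology.** The Introduction says psychological factors are likely involved, so adjustment may remove real signal. This stands, and it rules out making an anxiety-free result a condition for the primary conclusion.

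None of these points removes the complete overlap in objective 2.

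**Conclusion.** The point holds firmly for objective 2 and conditionally for objective 1. In objective 2, AF status and the peri-procedural setting coincide completely and the planned t-test is unadjusted, so a difference cannot be attributed to AF alone. In objective 1, bias is possible but depends on anxiety varying between patients and acting on both AF6 and the marker. No dedicated measure or adjustment is planned; the SF-36 mental summary and the AF6 worry item are weak proxies without a planned role.

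Size and direction are unknown and may differ by marker. The illustrative rates of 11% to 56% for objective 2 and 5% to 36% for objective 1 rest entirely on the assumed shifts and correlations, with one marker and a two-sided 5% test. They show that modest effects would matter, not that such effects exist. This is a worthwhile, low-cost improvement, and it is time-sensitive because stress at the draw cannot be recorded afterwards.

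**What to change.** 1. Record one 0-10 rating of current stress or anxiety at the blood draw, in patients and controls. Prespecify sensitivity versions of both primary analyses adjusted for it, reported beside the unchanged main analyses.
2. For objective 1, also report the association with the five-item AF6 sum without worry/anxiety (0-50) and with the modified EHRA class, beside the full AF6 sum. Label these as supportive, not as a condition for the conclusion.
3. Under Primary endpoint, state that objective 2 compares patients on the day before ablation with controls not awaiting a procedure. Under Hypothesis, limit the inference to central sensitisation accordingly.

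**Cost.** One extra question per participant, a few additional analyses and two edits to the text; no extra visit, sample or patient. The adjusted results may be conservative because anxiety is partly AF symptomatology. A single rating cannot fully remove the confounding, which is why the restated contrast in item 3 is needed even if items 1 and 2 are adopted.
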